Our emergency department sees an average of 150 cases of DKA per year and our center is involved in multiple clinical trials studying DKA management in children. Further, members of our group have been influential in developing a hospital-wide DKA protocol that is utilized both in the emergency department as well as in the inpatient setting to establish standardized and safe clinical care.

Glargine administration early in DKA management has been studied by our colleagues at University of Colorado Hospital in adults (with direct involvement from our co-mentor [name]). This group found that early administration of glargine in DKA resulted in a decreased rate of rebound hyperglycemia (33.3% versus 93.5%, $p < 0.001$ (14)). This data cannot be directly translated into the care of children in DKA, however, given the increased risk of complications in children such as cerebral edema and adverse events related to severe hypoglycemia. Therefore, without good pediatric data, the timing of glargine administration during the management DKA in children is left up to the discretion of the Diabetes Care Team and is, therefore, variable. Over the past 3-4 years, giving early glargine in DKA in children appears, anecdotally, to work well in the transition to subcutaneous insulin. It is viewed by many Diabetes providers to be a practical method and many are comfortable with this technique.

No data looking exclusively in children exist on whether early glargine administration in DKA management results in reduced rates of rebound hyperglycemia, is protective against recurrent ketogenesis, or how this relates to the risk of hypoglycemia. Further, no data exist on use of CGM technology in children treated for DKA. This detailed information will provide novel knowledge of blood glucose response both during treatment of DKA, and in the immediate phase following resolution of DKA, and help broaden our understanding of type 1 diabetes. CGM use in the hospital may also reduce the risk of hypoglycemic events and therefore improve patient safety.

IV. Research Methods:

A. Outcome Measure(s):

Primary outcome: Rate of rebound hyperglycemia within 12 hours (or until time to hospital discharge if less than 12 hours) after discontinuation of IV insulin on glucometer.

- Percent of patients with blood glucose > 180 mg/dL.
- Median blood glucose.

Secondary outcomes:

1. Rate of rebound hyperglycemia (as described in primary outcome) on CGM.

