- Upon diagnosis of DKA patients will begin rehydration with standard fluid therapy using an initial IV bolus of 10mL/kg of 0.9% saline.
- Fluid boluses may be repeated at the discretion of the treating physician to restore hemodynamic instability.
- During initial therapy, study personnel will obtain informed consent. .
- Participant Data: basic information such as name, date of birth, race/ethnicity, and diagnosis will be collected.
- Randomization:
 - We will use a blocked, stratified randomization scheme to allocate participants 1:1 to treatment groups. Randomization will be stratified within new onset and existing T1D patients to ensure balance across treatment groups.
 - Ideally, randomization will occur during the initial fluid bolus, however, if this is not possible then the patient will be treated with the standard DKA protocol for this study site until consent is completed, but not beyond the time frame outlined in the exclusion criteria.
 - Participants will be randomized into one of two groups:
 - 1. Early glargine, study group (N ~ 25):**
 - a. Administer glargine SQ x 1 when pH \geq 7.10.
 - b. Primary investigator and/or on-call co-investigator to determine glargine dose:
 - i. New onset T1D: 0.3 units/kg
 - ii. Established T1D: use home total daily dose (TDD) of long-acting insulin (or TDD of basal if on an insulin pump), converted to glargine equivalents.
 - 2. Standard-of-care, control group (N ~ 25):**
 - a. Administer glargine SQ x 1 at time of correction of acidosis (venous pH \geq 7.3 and serum bicarbonate \geq 18 or BHB \leq 1) and discontinuation of IV insulin.
 - b. Primary investigator and/or on-call co-investigator to determine glargine dose as described above.
- After initial fluid bolus(es), standard insulin therapy begins with a continuous infusion of IV regular insulin at a rate of 0.1 units/kg/hr.
- Ongoing rehydration is established using IV fluids with $\frac{3}{4}$ normal saline at a standard rate of 1.5 x maintenance unless this is determined to be harmful by the primary attending physician.
- Potassium replacement is provided using IV fluids containing potassium acetate and potassium phosphate.
- When serum glucose concentration declines below 250 mg/dL, dextrose (5-12.5%) is added to the IV fluids to maintain serum glucose between 100 mg/dL and 200 mg/dL.

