- If more than 12.5% dextrose IV fluids are needed to maintain serum glucose between 100 mg/dL and 200 mg/dL, the IV insulin rate will be decreased by 0.01 units/kg/hr.

Laboratory Monitoring during DKA treatment:

- Blood glucose concentration is obtained at presentation and hourly while on IV insulin using a point-of-care glucometer or serum measurements.
- Venous pH, serum electrolytes (Na, K, Cl, HCO₃, BUN, creatinine) are obtained at presentation and then every 2-4 hours while on IV insulin.
- Serum beta-hydroxybutyrate (BHB) will be obtained at presentation and then every 6 hours while on IV insulin until \leq 1.0 mmol/L.
- HbA1c will be obtained at presentation.

Continuous Glucose Monitoring (CGM): An option to have CGM sensor placed will be discussed with participant and/or primary guardian. The CGM system used during this study will be the Abbott FreeStyle Libre Pro Flash® Glucose Monitoring System (Figure 2).

Figure 2: Abbott FreeStyle Libre Pro Flash® Glucose Monitoring System:

<http://www.freestylelibrepro.us/blood-glucose-monitoring-device.html>

The FreeStyle Libre Pro® uses a small low-profile sensor approved for up to 14 days of wear in the USA by the FDA and has shown an average mean absolute relative difference (MARD) of 11.4% over 14 days of continuous wear. The Libre is also marketed as being free from interference with acetaminophen, eliminating this as a concern in our population as this is a common medication used in pediatrics. Further, this system does not require calibration and is blinded from the participant. Data will be available to study personnel at time of download after 1 week of wear.

CGM protocol:

- Following informed consent, an area on the back of the upper arm will be cleaned with an isopropyl alcohol solution and the CGM sensor system will be placed by trained study personnel.
- The CGM sensor placement will ideally occur after initial rehydration has been established, however, if this is not possible the CGM can be placed on the participant at any time during the initial 12 hours of DKA management.
- The CGM sensor will remain on the participant for the duration of hospitalization and an additional week following discharge.
- If a CGM sensor malfunctions during the participant's hospitalization, a new sensor can be replaced by study personnel as soon as possible following knowledge of the malfunction.

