In any clinical study unforeseen human factors provide challenges. This current study is based on a previous study in adults (14) with no reported adverse events such as increased hypoglycemia in those given glargine early in DKA management. However, the primary physician or Diabetes Team may decide to change the participant’s DKA management plan and they would, therefore, come off the study protocol. Additionally, the accuracy of a CGM (which samples interstitial fluid) when used in states of dehydration has not been well-studied. However, a number of small studies have shown CGM to be an accurate measure of blood glucose in an ICU setting (21,25). To improve CGM accuracy we will place the CGM only after initial intravascular hydration has been completed and the CGM will be calibrated (if needed) using a POC glucometer at least twice daily. Additionally, we will continue to obtain frequent POC glucometer readings throughout the hospitalization as this will be used to measure our primary outcome.

We have also performed careful power calculations to allow meaningful analyses of our data.

VII. Data Analysis Plan:

Table 1: Power calculations:

| | | | | | |
|---------------------------|-------|-------|-------|-------|-------|
| Significance level | 0.05 | 0.05 | 0.05 | 0.05 | 0.05 |
| Effect size (%) | 20 | 25 | 30 | 40 | 50 |
| Odds Ratio | 2.333 | 2.852 | 3.500 | 5.444 | 9.333 |
| Power (%) | 80 | 80 | 80 | 80 | 80 |
| Total N | 186 | 122 | 84 | 48 | 30 |

Per our power analysis (Table 1), with a total sample size of 48-50 (24-25 per group) we will have 80% power to detect an absolute difference of 40% in rebound hyperglycemia between the two study groups. These power analyses assume that 30% of participants in the early glargine group will experience rebound hyperglycemia. Chi-squared tests will be employed to evaluate whether the difference in rebound hyperglycemia between the two study groups is statistically significant. We will also use logistic regression to adjust for potential confounders (*BMI, sex, age, established T1D versus newly-diagnosed T1D*). Using a blocked and stratified randomization plan we expect to have similar numbers of newly-diagnosed T1D and known T1D patients in each group.

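### The supporting adjusted odds ratio for rebound hyperglycemia is planned without a small-sample method: it would be overstated at the design rates, and would have no finite value in about one trial in five if the adult result recurs

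*Combined protocol and SAP*

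**What the plan says.** Section VII (Data Analysis Plan) assigns the significance test for rebound hyperglycemia to chi-squared. It then adds a second, adjusted analysis: "We will also use logistic regression to adjust for potential confounders", listing BMI, sex, age and new-onset v established T1D. It names no penalised or exact fit, no rule for a model without a finite estimate, and no type of test or interval for the adjusted effect.

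The sample size rests on the unadjusted comparison: "with a total sample size of 48-50 (24-25 per group") the plan states that "we will have 80% power to detect an absolute difference of 40% in rebound hyperglycemia between the two study groups", and "These power analyses assume that 30% of participants in the early glargine group will experience rebound hyperglycemia". Section C.2.1 says the trial will "allocate participants 1:1 to treatment groups", stratified by new-onset v existing T1D.

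Section III gives the adult result behind the trial, a "decreased rate of rebound hyperglycemia (33.3% versus 93.5" per cent. Section VI says the present study builds on that adult study.

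**The concern.** Maximum-likelihood logistic regression has two known weaknesses in small samples. When there are few events or non-events per model term, the estimated odds ratio is biased away from 1. When one cell of the treatment-by-outcome table is empty, the treatment odds ratio has no finite estimate.

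Both bear on this trial. The reported adjusted odds ratio would tend to overstate the benefit. If early glargine works as well as it did in adults, there is also an appreciable chance that the planned model yields no usable odds ratio, and a Wald p-value that contradicts a decisive chi-squared test. The team would then have to choose another method after seeing the data.

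**Working it through.** **Inputs.** From section VII: two-group comparison, alpha 0.05, 80% power, 30% rebound on early glargine and a 40-point difference (so 70% in controls), 24 per arm, five model terms. From section III: 33.3% v 93.5%. Odds ratios are control relative to early glargine, the direction used in the section VII power table.

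**Reproducing the plan's figure.** Two-sided, pooled variance under the null, no continuity correction:

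n per arm = [1.96 × √(2 × 0.5 × 0.5) + 0.842 × √(0.3 × 0.7 + 0.7 × 0.3)]² / 0.4² = (1.386 + 0.545)² / 0.16 = 23.3, rounded up to 24.

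The total is 48, as stated. The odds ratio is (0.7/0.3) / (0.3/0.7) = 5.44, as stated. The same formula reproduces all five columns of the table.

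**Information per term.**
- Design rates: events 24 × (0.30 + 0.70) = 24, non-events 24; 24/5 = 4.8 per term.
- Adult rates: events 24 × (0.333 + 0.935) = 30.4, non-events 48 − 30.4 = 17.6. The scarcer outcome is now non-events: 17.6/5 = 3.5 per term. The true odds ratio is (0.935/0.065) / (0.333/0.667) = 28.8.

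**Chance that every control child rebounds.**
- Adult rates: 0.935^24 = 19.9% (0.935^25 = 18.6% with 25 per arm).
- 90% control rate: 0.9^24 = 8.0%.
- Design rates: 0.7^24 = 0.02%.

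**Simulation.** There were 4,000 to 6,000 trials per setting, 24 per arm, fitting treatment, BMI, sex, age and T1D status. The covariates had no effect on outcome; this is an assumption, because the documents give no covariate effects. Separation (no finite estimate) was checked directly. Maximum-likelihood (ML) summaries cover trials with a finite estimate.

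| Rates | True OR | ML median | ML geometric mean | No finite ML estimate | Firth geometric mean |
|---|---|---|---|---|---|
| 30% v 70% | 5.44 | about 6.9 | about 7.4 | 0.1-0.2% | 5.5-5.6 |
| 33.3% v 93.5% | 28.8 | about 41 | about 46 | 20-22% | 29.7 |
| 30% v 90% | 21.0 | about 34 | about 38 | 9-10% | 22.6 |

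At the design rates the geometric mean is 7.4/5.44 = 1.36 times the truth. Firth gave a finite estimate in every simulated trial. With moderate covariate effects (also assumed) the design-rate bias on the log scale was +0.33 to +0.39, against +0.30 to +0.32 without them.

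**What drives each problem.**
- Inflation at the design rates grows with the number of terms: geometric mean 6.0 with treatment alone, 6.3 adding T1D status, 7.1 with all covariates except BMI, 7.4 with all five terms.
- Separation at the adult rates does not: 20% with treatment alone, 21% with five terms. It comes from the all-event control arm.

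**Effect on tests at the adult rates.** Chi-squared rejected in 99.9% of simulated trials. The likelihood-ratio test of the ML model rejected in 99.7%. The Wald test rejected in only about 78%, because separated fits have very large standard errors.

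**The case against.** The strongest reply is that this is not the main test. Chi-squared is named first, the logistic model is an addition, and the powered effect is an absolute difference, which can still be estimated when all controls rebound. That stands: what may be lost is a finite odds ratio in a supporting model.

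It is also fair that the two problems belong to different scenarios. At the rates the trial is designed for, separation hardly occurs. The adult rates are not the design assumption, and section II cites rebound in roughly 40-90% of patients. The adult scenario is still not remote, since the protocol presents that study as its basis.

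Four stronger readings are tempting, and the documents do not support them:
- **That the choice of covariates causes the failure.** Separation is about 20% with no covariates at all, and BMI accounts only for the step from 7.1 to 7.4. Leaving out a severity measure neither inflates the odds ratio nor confounds a randomised comparison.
- **That BMI and sex should give way to a severity measure such as venous pH.** Any power gain depends on how strongly severity predicts rebound, and the documents give no figure for that. Nor do they say that BMI would be used unscaled for age. The four covariates are pre-specified and include the stratification factor.
- **That the adjusted test exceeds 5%.** In null simulations the likelihood-ratio test ran at about 6-7%, but the Wald test on the same fit ran at about 5-6%. The plan names neither.
- **That the primary conclusion is at risk.** Chi-squared works with an empty cell.

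**Conclusion.** The point holds as a recommendation about a supporting analysis. At 30% v 70% with 24 per arm, the planned adjusted odds ratio would typically be overstated: median about 6.9 and geometric mean about 7.4, against 5.44. At 33.3% v 93.5% it would have no finite value in about 20-22% of trials, or about 9-10% at 30% v 90%, and a Wald test would have about 78% power.

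The event counts and the 20% chance of an all-event control arm follow by arithmetic from the protocol's own figures. The size of the bias comes from simulation that assumes covariates without effect, linear BMI and age terms, and ordinary maximum likelihood. The last is inferred because no other method is named.

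Separation at the adult rates would be more frequent if fewer children were analysed: 24% at 22 per arm and 29% at 20 per arm. That is relevant because section IV.B removes children without confirmed T1D from the analysis.

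**What to change.** Keep the chi-squared test and the listed covariates, and specify the fitting method in section VII. For example:

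> The adjusted odds ratio for rebound hyperglycemia will come from a logistic model with treatment, BMI, sex, age and T1D status, fitted by Firth penalised likelihood. Its confidence interval and p-value will be based on the profile penalised likelihood.

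Do this before outcome data by arm are seen. Dropping covariates instead would reduce the inflation but would not cure separation.

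The cost is a sentence or two of text and slightly more analysis work, with no change to recruitment, data collection or treatment. The reported odds ratio will be less extreme than the maximum-likelihood one.

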- b. Assess the rate of blood glucose decrease while receiving IV insulin in children with DKA given early glargine versus standard-of-care management.
- c. Assess the number of participants who needed a decrease in their IV insulin rate between the two groups.

Hypothesis 4 (Exploratory): Continuous glucose monitoring (CGM) will be a feasible and useful tool during DKA treatment in children.

- a. CGM will agree with point-of-care (POC) blood glucose levels during DKA treatment in children.

Specific Aim 4 (Exploratory):

- a. To evaluate the agreement of CGM and POC glucose monitoring during DKA treatment in children.
- b. To determine the percent of CGM failures during DKA treatment in children.
- c. To describe the clinical importance of differences between CGM and POC glucose using Clarke error grid analysis.

In summary, this will be a clinical trial with aims to: 1) determine the rate of rebound hyperglycemia in children with DKA given glargine early in the treatment of DKA compared to those given glargine upon complete resolution of the metabolic acidosis (standard-of-care management); 2) evaluate the rate of recurrent ketogenesis in participants given early glargine compared to those given standard-of-care DKA management; 3) assess the risk of hypoglycemia between the two groups; and 4) evaluate the feasibility and utility of CGM as a tool to monitor blood glucose levels during DKA treatment in children.

The importance of this proposal relates to the research and clinical need to establish a smoother transition off of IV insulin in the management of DKA in children and to assess the utility of continuous glucose monitoring during treatment of DKA in children.

II. Background and Significance: *Explain the background of this project so that we will understand why it is important to perform this research project. (Approx. 1 page)*

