The data collected by CGM will be summarized for each patient and day into variables describing glycemia, such as mean glucose, area under the curve, area under the curve >180 mg/dL, and percent of time spent above or below particular glucose thresholds (e.g., >180, <60, and <70 mg/dL). Trends over time in these summary statistics will be evaluated graphically to give insight into blood glucose response during treatment of DKA and immediately after resolution of DKA. For variables without an excess of zero values, we will use linear mixed-effects models to compare trajectories over time in the two groups. We will also calculate the mean value of each of these statistics for each patient and compare the groups using t-tests or nonparametric equivalent. Bland-Altman plots will be used to evaluate the agreement between CGM glucose variables (e.g., mean glucose) and POC glucose. To interpret the clinical relevance of any discrepancies between the two sets of measures, we will use Clarke error grid analysis, which classifies pairs of blood glucose measurements made by two methods into categories based on the impact the discrepancy would have on treatment decisions.

VIII. Summarize knowledge to be gained:

Limited data suggest that administration of glargine early in DKA management may reduce rebound hyperglycemia, recurrent ketogenesis, and overall hospital length of stay; however, this has not been well-studied in children. Given the increasing incidence of T1D in youth, frequency of DKA, and hospitalizations secondary to DKA, a smoother transition to subcutaneous insulin could reduce in-hospital morbidity and overall cost per admission. Therefore, we propose to evaluate the effects of early glargine in pediatric DKA management. Additionally, there currently are no known studies using CGM technology in DKA in children evaluating rebound hyperglycemia and the transition to subcutaneous insulin. Therefore, these data will be vital in assessing our primary and secondary outcomes and in broadening our understanding of DKA management in this population.

IX. References:

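### The CGM analysis is specified by day and by patient mean, whereas the CGM outcomes are set in hours around IV insulin and Aim 4a concerns reading-level agreement

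*Combined protocol and SAP*

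**What the plan says.** **Outcomes (Section IV.A).** The primary outcome is rebound hyperglycemia "within 12 hours (or until time to hospital discharge if less than 12 hours) after discontinuation of IV insulin on glucometer". Secondary outcome 1 carries that definition over to CGM (percent of patients above 180 mg/dL, median glucose, percent of time above 180). Secondary outcome 3 includes percent of CGM time below 70 mg/dL on IV insulin and in the next 12 h, with no discharge clause. Secondary outcome 4 is the rate of glucose decrease on IV insulin, on glucometer and CGM, at 0-2, 2-4, 4-6 and >6 h.

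**Analysis (Section VII).** The stated unit is the day: "The data collected by CGM will be summarized for each patient and day into variables describing glycemia". Trends in these summaries are to be "evaluated graphically to give insight into blood glucose response during treatment of DKA and immediately after resolution of DKA". Then: "For variables without an excess of zero values, we will use linear mixed-effects models to compare trajectories over time in the two groups". The plan will also "calculate the mean value of each of these statistics for each patient and compare the groups using t-tests" or a nonparametric equivalent. No 12-hour or 2-hour window appears.

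**Agreement.** Specific Aim 4a is "To evaluate the agreement of CGM and POC glucose monitoring during DKA treatment in children". Section VII plans: "Bland-Altman plots will be used to evaluate the agreement between CGM glucose variables (e.g., mean glucose) and POC glucose". It adds "Clarke error grid analysis, which classifies pairs of blood glucose measurements made by two methods" to judge clinical relevance. It gives no rule for matching readings in time and none for repeated readings per child.

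**Wear.** Under the CGM protocol in C.2.1 the sensor stays on for the hospital stay plus one week. Wearing it is optional (Section IV.D).

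**The concern.** The outcomes and their analysis use different time units. The arms differ only in when glargine is given (Section IV.D), so most of a week of wear lies outside the hours that IV.A singles out. A mean over all of it would dilute a short-lived difference. Outcome 4 is a sharper case: one value per day holds no information on 2-hour rates, and Section VII is silent on rate of decrease on the glucometer too. Hypothesis 3b, part of the hypoglycemia-risk aim, rests on that outcome.

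For Aim 4a, the clinical question is how far a single CGM reading may lie from the POC value at that moment. Averaging cancels part of the reading error, so limits of agreement computed on means can look better than a clinician would experience. With windows, hour 0 and pairing left open, these choices could be made after the data are seen.

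**Working it through.** **1. The plan's own figure.** Section VII gives no sample size, power or precision for CGM. Its N is for the primary outcome, and it reproduces. With 30% against 70%, two-sided alpha 0.05 and 80% power, n per arm = [1.960·√(2·0.5·0.5) + 0.842·√(0.3·0.7 + 0.7·0.3)]² / 0.4² = 23.3. This rounds up to 24 per arm, 48 in total, as stated. Nothing below alters it.

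**2. Outcomes against analysis.**

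| IV.A outcome | Window in IV.A | What Section VII offers |
|---|---|---|
| 1, CGM rebound | 12 h (or to discharge) after IV insulin stops | daily summaries and a patient mean; the chi-squared test may cover percent of patients >180 |
| 3, CGM time <70 | all time on IV insulin plus 12 h | daily summaries and a patient mean; outside the mixed model if zeros are in excess |
| 4, rate of decrease | 0-2, 2-4, 4-6, >6 h on IV insulin | nothing named, on either device |

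The outcome 4 row needs no assumption.

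**3. Dilution if the patient mean covers all wear.** Length of stay is not given, so assume 8 days of wear in all. Then 12 h is 12/192 = 6.25% of the time (12/168 = 7.1% for 7 days, 12/240 = 5.0% for 10 days).

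For power, take a two-sample t-test at two-sided alpha 0.05 with 24 wearers per arm (assumed). A standardized difference of 0.826 in the window gives 80%. Split wear into h half-days of equal variance and pairwise correlation r, with the effect present in k of them. The difference in the mean becomes d′ = 0.826·(k/h) / √(r + (1−r)/h).

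| Summary | k (effect) | r = 0 | r = 0.5 | r = 0.8 |
|---|---|---|---|---|
| 8-day mean, h = 16 | 1 (12 h) | 10.8% | 5.7% | 5.4% |
| 8-day mean, h = 16 | 2 (24 h) | 28.8% | 7.7% | 6.7% |
| First 24 h after IV insulin, h = 2 | 1 (12 h) | 50.8% | 36.6% | 31.5% |
| First 24 h after IV insulin, h = 2 | 2 (24 h) | 97.7% | 89.9% | 84.0% |

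With 12 wearers per arm and the same difference, the windowed test itself has 49.0%, and the 8-day mean 5.2-7.7% for a 12 h effect.

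**4. The mixed model under the same assumptions.** Let day 1 start when IV insulin stops and let day be categorical. The contrast of day 1 with the other seven days has d″ = 0.826·(k/2) / √((1−r)(1/2 + 1/14)). With 24 per arm, power is about 46%, 75% and 98% (r = 0, 0.5, 0.8) for a 12 h effect, and 96-100% for a 24 h effect.

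**5. Agreement.** C.2.1 gives a mean absolute relative difference (MARD) of 11.4%. With unbiased normal error, SD = 11.4% / √(2/π) = 14.29%, which is 28.6 mg/dL at 200 mg/dL. Single-reading limits are then ±1.96·28.6 = ±56 mg/dL. For a mean of 12 pairs (assumed) with error correlation ρ within a child, multiply by √(ρ + (1−ρ)/12): ±16.2 at ρ = 0, ±41.2 at ρ = 0.5, ±49.2 at ρ = 0.75.

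**The case against.** The strongest reply is that this is loose wording and not a wrong analysis. IV.A fixes the windows and a reader may carry them into Section VII, which never defines a day and never says the patient mean spans the whole week. That stands, so the dilution in step 3 is conditional.

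A reader might infer from step 3 that the planned CGM comparisons as a whole have 5-11% power. The documents do not support that. The patient mean is an additional comparison; the mixed model comes first, and step 4 shows that it could recover much of the loss. The recovery has limits: it needs day to be categorical and suitably anchored, neither of which is stated, and the plan itself leaves variables with excess zeros out of the model. Time below 70 mg/dL is likely to be one.

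Nor does it follow that CGM rebound has no windowed test. The chi-squared sentence in Section VII speaks of rebound hyperglycemia without naming a device, so it can be read to cover the percent of children above 180 on CGM. It does not reach median glucose or percent of time. The 12 h share also does not describe outcome 3, whose window includes all time on IV insulin.

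On agreement, mean glucose is only an example, and the Clarke grid works on pairs, so reading-level comparison is not excluded. But the grid gives zone percentages, not bias or limits of agreement, and no matching rule is stated. The MARD is a 14-day average, not a DKA figure, so step 5 illustrates direction and rough size only.

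**Conclusion.** The point holds as a mismatch to reconcile before analysis. It is worth considering but does not threaten the trial. Two parts rest on the text alone: daily summaries cannot give outcome 4's 2-hour rates and Section VII names no analysis of that outcome on either device; and Bland-Altman on CGM variables such as mean glucose does not describe single-reading agreement.

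The power loss is conditional. It is severe for a mean over all wear and a 12 h effect (about 5-11% against 80%), and smaller or absent for a suitable day-1 contrast or for an effect lasting a day. Wear length, number of wearers, correlations, duration of effect and number of pairs are all assumed.

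These outcomes are secondary or exploratory, and the CGM parts rest on an optional subset. A reader might extend the point to the main result, but the primary outcome is measured on glucometer with its own test, and N = 48 reproduces.

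**What to change.** (a) **Windows.** Compute each between-arm CGM summary in its own IV.A window; for outcome 3 that is all time on IV insulin plus 12 h. Compare arms with the t-test or nonparametric test already planned. State that the chi-squared test also covers CGM percent of patients above 180. Keep daily and week-long summaries descriptive.

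(b) **Outcome 4.** On glucometer and CGM, compute the rate of decrease in the four listed steps, with hour 0 defined in advance. IV.A does not define it, and exclusion criterion 4 allows entry up to 6 h into IV insulin. If hour 0 is the start of the infusion, early steps will precede randomization for some children. Restrict the arm comparison to steps that begin after randomization, or report earlier ones separately, and give the number of children per step. Treat these as secondary results with no multiplicity claim.

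(c) **Agreement.** Run Bland-Altman on time-matched CGM-POC glucometer pairs during IV insulin, with a matching tolerance fixed in advance and limits that allow for repeated readings per child. Use the same pairs for the Clarke grid.

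The cost is wording and modest programming on data already collected. Limits of agreement may be wider. Early CGM steps may hold few children, because C.2.1 allows sensor placement up to 12 h into DKA management. Pairs will be fewer where the hourly glucose was a serum value.
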